#### 7.1.5.2 Data Collection

Study subjects will undergo screening and pre-procedure visits, and then follow-up visits at Discharge, and 30 Days (+14 days) for Endpoint analysis. Long-term follow-up data is collected at 6 Months (+/- 30 days), 1 Year (+/- 60 days), 2 Years (+/- 60 days), 3 Years (+/- 60 days), 4 Years (+/- 60 days), and 5 Years (+/- 60 days).

The Study Visit Schedule is outlined in Table 4 for enrolled subjects for the duration of the study from Screening and Baseline through the 30 Day visit (Primary Endpoint) and 5 year follow-up visits.

Table 2. Study Visit Schedule

	Screening	(≤30 days of procedure) Baseline	Procedure	Post-Procedure (Within 48 hours)	Discharge	30 Day Follow-Up (+14 days)	6 Month (+/-30 days)	1 Year (+/-60 days)	2-5 Years (+/-60 days)
Informed Consent	X								
Medical History	X								
Physical Exam	X				X	X		X	X
CSS Angina	X				X	X		X	X
NYHA Classification	X				X	X		X	X
STS Risk Score, Logistic EuroSCORE, and EuroSCORE II	X								
Operability Risk Assessment	X								
Cardiac Medications		X	X	X	X	X	X	X	X
Adverse Event Assessment			X	X	X	X	X	X	X
Frailty Assessment		X							
NIH Stroke Scale		X 		X 	X 	X 			
Modified Rankin Scale		X 		X 	X 	X 			
Six Minute Walk Test (6MWT)		X 				X 			
KCCQ Questionnaire		X				X			
Labs									

Hemoglobin, Hematocrit, Platelet Count and White Blood Cells		X		X	X	X			
PTT or PT/INR		X		X	X				
CK/CK-MB and/or Troponins		X 		X 		X			
Creatinine		X		X	X	X			
Liver Panel (ALT, AST)		X							
Albumin		X				X			
Non-Invasive Tests									
ECG		X		X	X	X		X	
Chest X-ray		X							
Transthoracic Echocardiogram (TTE)	X				X	X		X	X
Fluoroscopic imaging implanted valve			X			X 		X 	X 
Invasive Tests									
CT Thoracic/Abdomen with visualization of iliac and femoral arteries	X								
Cardiac Catheterization or CT angiogram	X								
Supra-aortic Angiogram or (TEE)	X		X						
Invasive hemodynamics			X						

 Collection of adverse events begins when the patient starts the procedure. This is defined as when anesthesia is first administered

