#### 7.1.6 Safety and Effectiveness evaluation methods

##### Primary Endpoint

The primary endpoint is all-cause mortality at 30 days post-index procedure.

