## **8. Statistical considerations**

### **8.1 Statistical design, method, and analysis procedures**

The clinical study is a single-arm prospective study intended to demonstrate the safety and performance of the SAPIEN 3 THV in the Chinese population.

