### **8.2 Sample Size**

The sample size of 50-60 patients is determined per Chinese regulatory requirements and agreement for a regional study of a medical device already approved in other regions based on a well-designed prospective study.

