### 8.3 Expected expulsion rate

The Chinese regulatory requirements determine 50 patients should meet the primary endpoint. If a minimum of 50 patients complete 30 Day visit and upto 60 patients have the procedure, the expected drop-out rate is <17%.

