### 8.4 Statistical method for all data, together with deficient, unused or fault data (including drop out and withdrawal) and method for treating unreasonable data

The primary and secondary endpoints will be reported based on the AT Population. Descriptive and summary statistical analysis will be performed on all endpoints. Patient listings for adverse events, deaths, and reinterventions will include all enrolled patients.

All clinically relevant baseline and follow-up variables will be tabulated. Descriptive statistics for continuous variables include mean, standard deviation, sample size, median, minimum, and maximum) and frequency tables or proportions for discrete variables.

Kaplan Meier estimates will be performed at the pre-specified follow-up times to project the estimates for time-related endpoints such as the 30-day mortality rate, the primary endpoint; the standard error and confidence limits will be computed using Greenwood's algorithm. Based on 50 patients as point estimate and length of estimate on the primary endpoint, the 30 days death rate and 95% confidence interval will be summarized.

Echocardiographic data will be analyzed by an Echo core laboratory with respect to the degree of total aortic valve regurgitation (TVR) and paravalvular aortic valve regurgitation (PAR) according to the VARC-2 definitions [29].

These data and other categorical data (e.g., NYHA class) will also be presented as shift from baseline for each of the pre-specified follow-up periods.

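### Section 8.4 bases the confidence limits for 30-day mortality on Greenwood's variance with no scale and no zero-event rule; with no deaths the interval is 0% to 0% or undefined, against an exact 0 to 7.1% (n=50)

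*Combined protocol and SAP*

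**What the plan says.** Section 7.1.6 defines the endpoint: "The primary endpoint is all-cause mortality at 30 days post-index procedure". Section 8.4 reports it in the As Treated (AT) population, estimates it by Kaplan-Meier, and states that "the standard error and confidence limits will be computed using Greenwood"'s algorithm. The next sentence begins "Based on 50 patients as point estimate and length of estimate on the primary endpoint" and ends by saying that "the 30 days death rate and 95% confidence interval will be summarized"; it names no interval method. No section says whether the limits are formed on the plain, log or log-log scale, and none says what is reported when there are no deaths.

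Section 8.1 describes a single-arm study "intended to demonstrate the safety and performance of the SAPIEN 3 THV in the Chinese population" and gives no hypothesis, performance goal or pass/fail rule. Section 8.2 sets the size by agreement with the regulator: "The sample size of 50-60 patients is determined per Chinese regulatory requirements". Section 8.5 leaves further statistical detail to a SAP; the document contains no separate SAP text.

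**The concern.** Greenwood's variance is a sum over death times. With no deaths the sum is empty, and the formula reports no uncertainty at all, whatever the number of patients. With 50 to 60 patients and a 30-day endpoint, zero or very few deaths is a realistic outcome if the true rate is low. With one to three deaths the limits depend heavily on a scale that the plan does not state.

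Because there is no test or performance goal, the 30-day death rate and its 95% interval are the primary result, and section 3.1 says the data are meant for Chinese regulatory approval. At stake is the stated precision of that result. A later choice of scale or substitute method, made once the deaths are known, would be a post hoc choice on the primary endpoint.

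**Working it through.** **Inputs.** n = 50 (8.4) and up to 60 (8.2); 95% level (8.4), taken as two-sided because the plan does not say; Kaplan-Meier with Greenwood (8.4). The documents give no expected death rate, so a range is assumed below.

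**The plan's own figure.** The only derivable figure in section 8 is the drop-out bound in 8.3: 1 − 50/60 = 16.7%, which agrees with the stated figure of less than 17%.

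**Zero deaths.** Greenwood: Var[S(t)] = S(t)² × Σ dᵢ / [nᵢ(nᵢ − dᵢ)]. If every dᵢ = 0, the sum is 0 whatever the numbers at risk, so S = 1 and SE = 0.
- Plain scale: 0 ± 1.96 × 0 gives 0% to 0%. The log scale gives the same.
- Log-log scale: log(−log 1) does not exist, so there is no interval.
- Exact (Clopper-Pearson) upper limit: 1 − 0.025^(1/n), which is 7.1% for n = 50 and 6.0% for n = 60.

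**How likely zero deaths is.** P(0) = (1 − p)ⁿ at assumed true rates:

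| True rate | 1% | 2% | 3% | 5% | 6% | 8% | 10% |
|---|---|---|---|---|---|---|---|
| n = 50 | 61% | 36% | 22% | 8% | 4.5% | 1.5% | 0.5% |
| n = 60 | 55% | 30% | 16% | 5% | 2.4% | 0.7% | 0.2% |

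**One to three deaths, n = 50, no censoring before day 30.** Here Greenwood's variance reduces to p̂(1 − p̂)/n. For one death, SE = √(0.02 × 0.98/50) = 1.98%, and the plain limits are 2% ± 3.88%.

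| Deaths | Plain | Log-log | Exact |
|---|---|---|---|
| 1 | −1.9 to 5.9% | 0.3 to 13.4% | 0.05 to 10.6% |
| 2 | −1.4 to 9.4% | 1.0 to 15.1% | 0.5 to 13.7% |
| 3 | −0.6 to 12.6% | 2.0 to 17.5% | 1.3 to 16.5% |

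The plain upper limit lies below the exact one. The log-log limits lie above the exact ones at both ends.

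**Coverage.** For each true rate, sum the binomial probabilities of the death counts whose interval contains it (no censoring):

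| True rate | 1% | 2% | 3% | 5% |
|---|---|---|---|---|
| Plain Greenwood, n = 50 | 39.5% | 63.5% | 78.1% | 92.0% |
| Plain Greenwood, n = 60 | 45.2% | 70.1% | 83.7% | 80.6% |
| Exact, n = 50 | 98.6% | 98.2% | 98.3% | 98.8% |

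At n = 50 and rates of 1 to 5%, almost all the shortfall is the zero-death case; given at least one death, plain limits cover 99.6 to 100%. That does not hold everywhere. At n = 60 and 5%, the plain interval for one death stops at 4.9%, so it misses too: P(0) + P(1) = 4.6% + 14.6% = 19.2% of the 19.4% non-coverage. At 6, 8 and 10% with n = 50, plain coverage is 80.7, 91.2 and 87.9%.

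**Early censoring.** As a bounding case, 60 patients were simulated with 10 given a censoring time before day 30 (uniform death and censoring times assumed, 40,000 runs per rate). Plain Greenwood covered 42.4, 67.1, 81.4 and 90.1% at 1, 2, 3 and 5%; the beta product procedure covered 98.1 to 98.6%. This is not a forecast. The 30-day visit window opens at day 30 (7.1.5.2), so a missed visit need not mean censoring before then.

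**The case against.** The strongest reply is that the scale and the zero-event rule are details that section 8.5 leaves to the SAP, which is versioned and re-approved before analysis. That is fair, and the finding is therefore limited to 8.4. But 8.4 does not leave the interval method open. It names Greenwood without qualification, and no Greenwood scale gives a usable upper limit at zero deaths.

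Second, the sentence about 50 patients may intend a simple proportion with a binomial interval. The wording does not exclude that, but it names no method, so Greenwood remains the only one named.

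Third, the low coverage figures are for plain limits, a scale the plan does not specify. This stands: with log-log limits plus an exact limit at zero deaths, coverage at n = 50 is 91.1, 98.2, 93.7 and 96.2% at 1, 2, 3 and 5%. The fault lies in the unstated scale and the missing zero-event rule, more than in Greenwood's variance itself.

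Fourth, the patients are at high surgical risk; if true mortality is 6 to 10%, zero deaths in 50 has a probability of only 4.5 to 0.5%. This stands as well, although plain limits under-cover there too.

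Finally, no decision depends on the interval, and deaths are listed by patient, so a reader could rebuild an exact one. That limits the severity but does not justify a 0% to 0% interval on the primary endpoint.

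**Conclusion.** The concern holds, at the level of something that should be fixed. As written, 8.4 gives a 0% to 0% interval or none if nobody dies, where the data would support an upper limit of 7.1% (n = 50) or 6.0% (n = 60). With one death in 50, the unstated scale alone moves the upper limit from 5.9% to 13.4%.

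The zero-death result follows from the formula and needs no assumption. The exact limits assume that all patients are followed to day 30; earlier censoring raises them (with zero deaths and 55 of 60 still at risk at day 30, 6.5%). The AT population could slightly exceed 60, because only patients who leave the procedure room with the valve count toward that cap (7.1.5.1), which would lower the bound a little. How often the problem would arise depends on a true rate that the plan does not give. A SAP outside this document could already supply the missing rule.

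**What to change.** In 8.4 and the SAP, name one interval for 30-day mortality that is valid with zero or few events and under censoring. For example: *The two-sided 95% CI for 30-day all-cause mortality in the AT population will use the beta product confidence procedure on the Kaplan-Meier estimate.* Without censoring before day 30 this is the Clopper-Pearson interval.

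A simpler alternative keeps Greenwood: state the log-log scale and, at zero deaths, report an upper limit of 1 − 0.025^(1/m), where m is the number at risk at day 30. Its weakness should be stated: at n = 50, coverage falls to about 91% near a 1% true rate and to about 87% just below 0.28%.

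Apply the same rule to any 30-day secondary safety event reported with Kaplan-Meier limits, and list those events, since 8.4 does not.

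The cost is one sentence. Endpoint, population and sample size do not change. The beta product interval is wider than plain Greenwood and somewhat conservative: without censoring, its coverage over true rates of 1 to 10% is 95.1 to 99.6% (n = 50) and 95.7 to 99.6% (n = 60).

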### 8.5 Procedures for reporting deviation from the original statistical plan

More detailed information regarding the statistical methods and analysis will be presented in the Statistical Analysis Plan (SAP). Statistical method changes and/or deviation from the original statistical analyses plan will be documented in the section of amendment of the versioned SAP which requires re-approval before the performance of analyses and to be included in the final study report.

### 8.6 Criteria and reasons for selection of subjects incorporated into analysis

All patients documented as part of the roll-in patient strategy will not be included in analysis population and will be evaluated separately.

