### 7.1.2 Selection of test methods and reasons

This is a prospective, single-arm, multi-center study to assess the safety and effectiveness of the SAPIEN 3 THV. Up to 60 patients will be enrolled and implanted with the device at four sites in China over an estimated six-month enrolment period with a follow-up period to 5 years. The study is expected to last 5.5 years.

An Echocardiography Core Lab will be established for standardizing echocardiographic secondary endpoints. A Medical Reviewer will review all endpoint-related adverse events.

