### 7.1.4 Selection of subjects (including selection of control group if necessary)

To ensure that a minimum of 50 patients are implanted with the SAPIEN 3 THV and complete the 30 Day follow-up for Primary Endpoint, up to 60 patients will be enrolled and implanted with SAPIEN 3 THV. Each site may not contribute more than 25 implanted patients to the study population. All patients will be followed for 5 years.

Enrolment will be closely monitored to ensure not more than 60 patients are implanted with SAPIEN 3 THV.

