#### 7.1.5 Patient Screening and Data Collection

##### 7.1.5.1 Patient Screening and Enrolment

The study site shall have a committed Heart Team involved in the screening process. The Heart Team will include at least two cardiac surgeon, one interventional cardiologist, one radiologist, and one anesthesiologist but could also include (without being limited to) the following specialties:

- Echocardiography
- Gerontology

The screening of patients in cardiovascular and cardiac surgery departments will be conducted by one or more delegated study team members. The study team will be responsible for ensuring and reporting study patient screening for study eligibility. Cumulative screening and enrollment logs will be maintained by study sites. Reasons for screen failures will be documented in study logs.

To accommodate the implant procedure learning curve, a roll-in strategy will be available. Each study site will be allowed up to two roll-in patients. Edwards Lifesciences will document if the patient is a roll-in patient before the implant procedure begins. Roll-in patients will complete all study visits and procedures, and not be counted toward the 60 implanted patients.

In addition, the Heart Team will be required to assess all patients for study inclusion to ensure compliance to surgical risk criteria, screening procedures to assess valve size and delivery method, and other inclusion/exclusion criteria. After heart team identifies a patient, the Sponsor will review and confirm eligibility during the case review process.

All patients who sign a study informed consent will be entered into the database. Subjects will be included

in analysis of the trial if an Edwards' investigational device is inserted into the patient. Only patients that leave the procedure room with a SAPIEN 3 THV in place will be counted toward the 60 implanted patients.

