#### Analysis Sets

- *As Treated (AT) Population*: all patients that were enrolled in the trial for whom the SAPIEN 3 valve implant procedure was begun, defined as the time in which the first Edwards' investigational device is inserted into the patient.

- *Valve Implant (VI) Population:* all AT patient who received and retained the SAPIEN 3 valve upon leaving the procedure room

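### Are roll-in patients let into the As Treated set, or past the limit of 60, because the exclusion in section 8.6 is not repeated elsewhere?

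*Combined protocol and SAP*

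**What the plan says.** Two parts of the combined protocol and SAP deal with roll-in patients expressly.

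- Section 7.1.5.1 (Patient Screening and Enrolment): "Each study site will be allowed up to two roll-in patients". The sponsor records roll-in status before the implant procedure starts. On the count, "Roll-in patients will complete all study visits and procedures, and not be counted toward the 60 implanted patients".
- Section 8.6 opens with the rule that "All patients documented as part of the roll-in patient strategy will not be included in analysis population and will be evaluated separately".

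Other parts touch the same ground without mentioning roll-ins.

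- Under the Analysis Sets subheading of 8.6, AT is "all patients that were enrolled in the trial for whom the SAPIEN 3 valve implant procedure was begun". The Valve Implant set is a subset of AT.
- Later in 7.1.5.1, subjects are included "in analysis of the trial if an Edwards' investigational device is inserted into the patient".
- Section 7.1.2: "Up to 60 patients will be enrolled and implanted with the device at four sites in China". Sections 7.1.4.4 and 8.2.1.1 repeat the limit of 60.
- Section 7.1.4: "Enrolment will be closely monitored to ensure not more than 60 patients are implanted with SAPIEN 3 THV".
- Section 8.3 derives its drop-out figure from the same numbers: "If a minimum of 50 patients complete 30 Day visit and upto 60 patients have the procedure", expected drop-out is below 17%.

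Section 8.4 reports the primary and secondary endpoints on AT, and lists adverse events, deaths and reinterventions for every enrolled patient. Section 8.5 leaves further statistical detail to a versioned SAP.

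**The concern.** The primary result is 30-day all-cause mortality in AT, intended for a regulatory submission. A programmer who built the AT flag from its definition alone would admit any enrolled patient in whom a device was inserted, roll-ins included. One who started from the first sentence of 8.6 would leave them out. Roll-ins exist to absorb the learning curve, so their outcomes may differ from those of the main cohort.

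The limit on implants raises a similar question. Section 7.1.4 reads as a ceiling of 60 on everyone receiving the valve, while 7.1.5.1 puts roll-ins outside that number. If the 60 did include roll-ins, fewer main-cohort patients would remain and the drop-out margin in 8.3 would be thinner than stated.

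Finally, both AT and the listings depend on the word enrolled. If roll-ins are enrolled, the AT definition taken alone admits them. If they are not, their deaths and adverse events might seem to fall outside the listings.

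**Working it through.** **The plan's own figure.** Inputs: 50 completers and 60 treated (8.3). Drop-out = (60 − 50)/60 = 10/60 = 16.7%, which is below 17%. The figure reproduces with the 60 made up of main-cohort patients only, as 7.1.5.1 provides.

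**How many roll-ins.** Inputs: four sites (7.1.2) and up to two roll-ins per site (7.1.5.1). Maximum = 4 × 2 = 8. If every slot is used and every patient keeps the valve, total implanted = 60 + 8 = 68.

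**The analysis set, text against text.**

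1. The exclusion is the first sentence of 8.6, the section that decides who enters the analysis. AT and Valve Implant are defined beneath it, so it governs both.
2. The exclusion names roll-ins, whereas the AT definition and the inclusion sentence in 7.1.5.1 are general. The specific rule limits the general ones.
3. Status is recorded before the procedure, so the exclusion cannot depend on outcome.

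Taken together, AT excludes roll-ins.

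**The limit, text against text.** Section 7.1.5.1 says in terms that roll-ins do not count toward the 60. Sections 7.1.2, 7.1.4, 7.1.4.4 and 8.2.1.1 state the same limit in short form without repeating the exception. Scenarios in which the 60 includes roll-ins, such as (60 − 8 − 50)/(60 − 8) = 2/52 = 3.8% permissible loss, rest on a reading that 7.1.5.1 rules out. Section 8.3 needs no recalculation.

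**What a wrong reading would cost.** Suppose an analyst did put all 8 roll-ins into AT. They would form 8/68 = 11.8% of the set. The documents give no expected mortality, so the death counts here are assumptions, with exact (Clopper-Pearson) 95% limits and every treated patient assumed to keep the valve:

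- Without roll-ins: 2/60 = 3.3% (0.4 to 11.5%), a width of 11.5 − 0.4 = 11.1 points.
- With 0 deaths among the 8: 2/68 = 2.9% (0.4 to 10.2%), shift 2.9 − 3.3 = −0.4 points.
- With 1 death: 3/68 = 4.4% (0.9 to 12.4%), shift 4.4 − 3.3 = +1.1 points.
- With 2 deaths: 4/68 = 5.88% (1.6 to 14.4%), shift 5.88 − 3.33 = +2.5 points.

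Each shift is well inside the interval for the main cohort.

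**Visibility of roll-in events.** Every patient who signs consent is entered in the database, roll-ins attend all study visits (both 7.1.5.1), and 8.6 has them evaluated separately. Their deaths are therefore collected and assessed however narrowly enrolled is read.

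**The case for a change.** The best case for a change is that inferable intent is not a definition. Section 8.6 excludes roll-ins from an unnamed analysis population and then defines two sets, neither of which mentions them. In 7.1.5.1 the exception covers only the count, and the unqualified inclusion sentence comes after it, so someone reading that section alone could conclude that roll-ins are analysed but not counted. The ceiling in 7.1.4, taken literally, is broken once 60 main-cohort patients and one roll-in are implanted. The remedy would be a few words, and a separate SAP would not amend protocol text.

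Much of this is accurate as description. The AT definition and the inclusion sentence lack the phrase, and the largest total that may be implanted (68) is never written down. What does not stand is the step from omission to conflict. Nobody building AT would bypass the opening sentence of the section that defines it, and the exception to the 60 is given expressly. The point about enrolled is weaker still: the table of contents lists an Appendix A of definitions that is not in the text available here, so the term cannot be called undefined.

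**Conclusion.** No change to the plan follows. A sponsor applying the document as written would keep roll-ins out of AT, evaluate them separately, recruit up to 60 main-cohort patients with up to 8 roll-ins in addition, and report the same primary result. The figures 50, 60 and under 17% all stand. What remains is an editorial gap: an exclusion stated once and not repeated wherever it applies. Repeating it would be harmless but would alter no number, result or conclusion.

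This rests on reading 8.6 as a whole, on the express exception in 7.1.5.1, and on roll-in status being documented before each procedure as required. The size of a misreading (8 patients at most, about −0.4 to +2.5 points on mortality) depends on the assumed death counts. A larger excess of deaths among roll-ins would shift the pooled figure further, but those deaths would also be visible in the separate evaluation. The primary analysis is an estimate with a 95% confidence interval and no pass/fail threshold, so there is no decision for the wording to tip.
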